A key concern with the dengue vaccine is the potential side effects, including transient vaccine viremia. After receiving the Qdenga vaccine, 49% of previously uninfected participants and 16% of those previously infected with dengue experienced vaccine viremia. This viremia typically began in the second week post-vaccination, lasted an average of four days, and was associated with mild to moderate symptoms such as headache, joint pain, muscle pain, and rash in some subjects. During this period, dengue diagnostic tests may yield positive results, making it difficult to distinguish between vaccine viremia and wild-type dengue infection. A study on IgG, IgM, and nonstructural protein 1 (NS1) response profiles post-Qdenga vaccination indicated that IgM and IgG profiles within 30 days of vaccination were similar to those observed during natural dengue infections, though no NS1 antigen was detected. As previously proposed that lower dose of vaccine might be associated with possible extra benefit of experiencing fewer side effects or risk of allergy, intradermal reduced dosed sound compelling.

Qdenga vaccine was also called TAK-003/DENVax in previous study, it was based on a live-attenuated DENV-2 strain (PDK-53-V) in which the premembrane (prM) and envelope (E) genes have been replaced by the homologous genes from each one of the four DENV serotypes. The recommendation for using the subcutaneous route in dengue vaccine administration is based on findings from certain Phase I studies. One such study assessed the safety and immunogenicity of a recombinant live attenuated tetravalent dengue vaccine (DENVax) in 96 flavivirus-naive healthy adults in Colombia. Participants in this study were randomized to receive either a high-dose formulation of DENVax or a placebo via

subcutaneous or intradermal injection. The study results indicated that both intradermal and subcutaneous routes elicited tetravalent dengue immune responses. However, the subcutaneous route was associated with a lower incidence of local adverse events compared to the intradermal route, although the difference was not statistically significant..

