### 5.7.3 Study samples

#### 5.7.3.1 Inclusion Criteria

1. Thai adult aged 18-60 years with positive dengue IgG from screening test, who not previously received dengue vaccine.
2. The subjects are able to and willing to comply with the requirements of the clinical trial program and could complete the 3-month follow-up of the study.
3. Individuals who are in good health condition at the time of entry into the trial as determined by medical history, physical examination and clinical judgment of the investigator and meet the requirements of immunization
4. The subject can provide with informed consent and sign informed consent form

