## Study flow

## Study procedure

Study period	Screening	Treatment	Treatment	Follow up	
		Vaccine dose 1	Vaccine dose 2	Day 30 ± 3 day	Day 120 ± 3 days
Day/week	Day 0 to -7	Day 0	Day 90 ± 3 days	Day 30 ± 3 day	Day 120 ± 3 days
Informed consent, medical history	X				
Contraceptive counselling	X				
Screen dengue IgG	X				
Review of Inclusion/exclusion criteria		X	X		
Physical examination		X	X		
Body Weight/ Height/ Vital sign		X	X		
Concomitant medication check		X	X		

Blood collection*		X	X		X
Randomization		X			
Vaccination		X	X		
Adverse event check (also by google form+/- telephone at 7, 30 day after each vaccination)		X		X	X

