#### 5.7.11 Ethical Consideration

- **Informed consent process**

1. The research team will announce and publicize the study through the Line account (@psucrc) and the Clinical Research Center website to invite individuals who may be interested in participating. Participants may contact the investigators or study nurses at any time if they have questions or concerns.
2. Individuals who wish to participate may register their interest through the Line account (@psucrc) or by emailing [contact]
3. The study nurse will provide the participant information sheet and invitation documents through a method convenient for the potential participant (e.g., email or Line). Those who agree to participate will sign the consent invitation document and return it to the Clinical Research Center.
4. The study nurse will schedule study visits according to the protocol. Appointments will be arranged on weekends or public holidays to facilitate participation and avoid the need for participants to take leave from work.
  - Transient vaccine viremia may occur following Qdenga vaccination. This condition has been reported in approximately 16% of individuals with prior dengue infection and 49% of those without previous dengue exposure. Symptoms typically begin during the second week after vaccination and last an average of four days. Reported symptoms

include headache, joint pain, myalgia, and rash. This event is less commonly observed after the second vaccine dose

- This study does not introduce additional risks beyond those associated with the standard use of the Qdenga vaccine, which is already approved for use in Thailand. Participants will be monitored and managed according to standard clinical practice. In the event of allergic reactions or other discomfort, investigators will provide appropriate medical care.
- Blood collection may cause mild discomfort at the puncture site, minor bleeding, or bruising lasting 3–4 days. Infection at the puncture site is rare. Some individuals may experience dizziness or fainting, particularly those with needle or blood phobia. These risks will be minimized by having experienced nursing staff perform all blood draws.

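### Scheduled adverse-event contacts at days 7 and 30 after each dose leave the typical window for vaccine-viraemia symptoms (about days 8 to 18) to be covered by recall

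*Combined protocol and SAP*

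**What the plan says.** The adverse-event row of the Study procedure table (section 5.7.10) reads "Adverse event check (also by google form+/- telephone at 7, 30 day after each vaccination". The word 'also' matters: the remote contacts are additional to checks marked at the visits. As extracted, the row is marked at Day 0, Day 30 ± 3 and Day 120 ± 3, and not at the dose 2 visit (Day 90 ± 3).

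Section 5.5 introduces the risk with "A key concern with the dengue vaccine is the potential side effects, including transient vaccine viremia". On timing it says "This viremia typically began in the second week post-vaccination, lasted an average of four days", and it describes the viraemia as "associated with mild to moderate symptoms such as headache, joint pain, muscle pain, and rash in some subjects". Section 5.7.11 repeats the timing among the risks to participants: "Symptoms typically begin during the second week after vaccination and last an average of four days". It gives the frequency as "approximately 16% of individuals with prior dengue infection and 49% of those without previous dengue exposure" and adds "This event is less commonly observed after the second vaccine dose".

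Section 5.7.3.1 admits only a "Thai adult aged 18-60 years with positive dengue IgG from screening test", so the lower of the two frequencies is the relevant one. Section 5.7.6 plans 24 participants, 12 per group. The secondary objective in section 5.4 is the safety and reactogenicity of the intradermal route. Section 5.7.8 lists adverse events after vaccination as a dependent variable. The text describes no diary, symptom list, onset-date field or recall period.

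**The concern.** The protocol names a particular systemic risk and says when it typically occurs, yet its contact schedule steps over that period. The day-7 contact comes before the typical onset. The next contact comes well after the typical episode has ended.

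At stake is the quality of the evidence for the secondary objective. Section 5.5 hypothesises that systemic adverse effects after the intradermal dose will be acceptable. For this risk, the supporting data would be what participants remember, some weeks on, of short illnesses of mild to moderate severity. Recall of that kind may lose some events and is likely to date the rest poorly. Loss of events would lean towards the hypothesised result. With no dated symptom list, it would also be hard to tell afterwards whether a reported headache or rash fell in the viraemia window at all.

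**Working it through.** The plan states no figure to reproduce here. The check compares two sets of dates and then sizes the result.

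**1. Typical symptom window** (sections 5.5 and 5.7.11)
- Onset in the second week, read as days 8 to 14, with a mean duration of 4 days.
- End = onset + 4: 8 + 4 = day 12 at the earliest, 14 + 4 = day 18 at the latest.
- Counting the onset day as day 1 of the four brings the ends forward by one day, to days 11 to 17.
- Reading the second week as days 7 to 13 puts the latest end at day 16 or 17. Only a day-7 onset would then coincide with a contact.

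**2. Contact days after each dose** (Study procedure table)
- Remote: days 7 and 30.
- Visit after dose 1: Day 30 ± 3, so 27 to 33 days after dosing.
- Visit after dose 2: Day 120 ± 3 against dosing on Day 90 ± 3. Earliest 117 − 93 = 24 days after dosing; latest 123 − 87 = 36 days.

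**3. Comparison**
- No remote contact or visit falls within days 8 to 18. Even the earliest permitted visit (day 24 after dose 2) is later than day 18.
- For symptoms starting on day 14 to be still present at day 24 they would have to last 24 − 14 = 10 days. To reach day 30 they would have to last 16 days. The stated mean is 4.
- Recall from the end of a typical episode to day 30: 30 − 18 = 12 days to 30 − 12 = 18 days (up to 19 with the onset day counted as day 1). From onset: 30 − 14 = 16 to 30 − 8 = 22 days.

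**4. How many participants this could concern**
- Expected viraemic participants among intradermal recipients after dose 2, if the 16% applied in full: 12 × 0.16 = 1.92. Probability of at least one: 1 − 0.84^12 = 87.7%.
- This is an upper bound on an expected count. The protocol says that viraemia is less common after dose 2, and that only some viraemic subjects have symptoms. It gives neither proportion.
- Illustration with assumed rates: at 8%, 12 × 0.08 = 0.96 expected and a 63% chance of at least one; at 4%, 12 × 0.04 = 0.48 and 39%.

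**5. Effect of a form at day 18**
- Recall from the end of a typical episode: 18 − 18 = 0 to 18 − 12 = 6 days.
- Forms: 24 participants × 2 doses = 48.

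**The case against.** The strongest reply is that a gap between contacts is not a gap in capture. The day-30 check can collect anything since the previous contact; no recall period is stated, so none is excluded. Trained staff also see participants about 30 days after each dose, so collection is not only remote. Section 5.7.11 lets participants approach staff whenever they wish and promises monitoring under standard practice. The study-flow content and the consent pages are not in the available text, and an instruction to report symptoms could be there.

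Most of this stands. A reader might infer that events will be missed. The documents do not show that; they show reliance on delayed recall. The open line to staff is offered for questions and concerns and is not described as a way of collecting adverse events, so it softens the gap without closing it.

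A reader might also apply 16% to all 24 participants and expect 24 × 0.16 = 3.84 cases. That count belongs to dose 1, which is subcutaneous in both arms, so it does not bear on the safety of the intradermal route. Moreover, 16% is a rate of viraemia, whereas an adverse-event form collects only symptoms.

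Finally, both arms follow the same schedule, and nothing in the documents suggests that under-reporting would differ between them. The comparison by arm is therefore not shown to be biased. The weakness lies in describing how often these symptoms follow intradermal dosing, and when.

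**Conclusion.** The concern holds as a weakness in the timing of data collection. It is not an internal contradiction, and it touches neither primary objective. On the protocol's own description, the typical window for the symptoms of a risk that it calls a key concern contains no scheduled contact after either dose, and the information would be recalled about 12 to 18 days after a typical episode ended.

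The size is modest. After dose 2, fewer than about 1.9 symptomatic participants would be expected among the 12 intradermal recipients, possibly fewer than one. In an arm of 12, however, each participant recorded or lost moves the observed proportion by 1/12 = 8.3 percentage points.

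The conclusion assumes that the second week means about days 8 to 14, that the four-day mean describes a typical episode (it is not an outer limit), and that no extra contact appears only in the missing figure. Under-reporting is a possibility, not a finding. Fever is not among the symptoms that the protocol attributes to viraemia, so the point should not be read as one about undetected febrile illness.

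**What to change.** In the adverse-event row of the Study procedure table:
- Add one online form after each vaccination near the end of the window, at about day 18. It should ask for onset and end dates of the four symptoms that the protocol lists: headache, joint pain, myalgia and rash.
- Keep the day-7 and day-30 contacts, and ask for the same dates on the day-30 form.
- In section 5.7.12, state that events with onset after day 7 following dose 2 will be reported by arm.

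If the study-flow figure already shows a contact in weeks 2 to 3, aligning the table with it and adding the dated symptom list would be enough.

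The cost is about 48 short forms through the system already in use, a small burden on participants and a possibly higher reported event rate; no visit is added. The gain is a typical recall of about 0 to 6 days. That is shorter, but it is still recall, and it does not amount to detection during the episode. Adding dated symptoms to the day-30 form alone would cost less, but would leave the 12 to 18 days of recall unchanged.

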### Arms and Interventions:

Arm 1: subcutaneous Qdenga for 1st vaccination then intradermal Qdenga for 2nd vaccination

Arm 2: subcutaneous Qdenga for 1st vaccination then subcutaneous Qdenga for 2nd vaccination

#### 5.7.11 Ethical Consideration

- **Informed consent process**

1. The research team will announce and publicize the study through the Line account (@psucrc) and the Clinical Research Center website to invite individuals who may be interested in participating. Participants may contact the investigators or study nurses at any time if they have questions or concerns.
2. Individuals who wish to participate may register their interest through the Line account (@psucrc) or by emailing [contact]
3. The study nurse will provide the participant information sheet and invitation documents through a method convenient for the potential participant (e.g., email or Line). Those who agree to participate will sign the consent invitation document and return it to the Clinical Research Center.
4. The study nurse will schedule study visits according to the protocol. Appointments will be arranged on weekends or public holidays to facilitate participation and avoid the need for participants to take leave from work.
  - Transient vaccine viremia may occur following Qdenga vaccination. This condition has been reported in approximately 16% of individuals with prior dengue infection and 49% of those without previous dengue exposure. Symptoms typically begin during the second week after vaccination and last an average of four days. Reported symptoms

include headache, joint pain, myalgia, and rash. This event is less commonly observed after the second vaccine dose

- This study does not introduce additional risks beyond those associated with the standard use of the Qdenga vaccine, which is already approved for use in Thailand. Participants will be monitored and managed according to standard clinical practice. In the event of allergic reactions or other discomfort, investigators will provide appropriate medical care.
- Blood collection may cause mild discomfort at the puncture site, minor bleeding, or bruising lasting 3–4 days. Infection at the puncture site is rare. Some individuals may experience dizziness or fainting, particularly those with needle or blood phobia. These risks will be minimized by having experienced nursing staff perform all blood draws.

#### **5.7.12 Data management and data analysis**

Data will be recorded in case record forms and subsequently entered into an electronic database using Microsoft Excel. Statistical analyses will be performed using the R software environment.

#### **Data analysis**

(1) Record and analyze data: using the R program version 3.5.1

(2) Analysis data:

- Continuous variables using Mean  $\pm$  SD or Median (IQR)
- Discrete variables using percentage
- Compare qualitative variables data using Pearson's Chi-squared test or Fisher's exact test
- Compare quantitative variables data using Student's t-test or Wilcoxon rank-sum test
- A probability value (P) <0.05 was considered significant

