### Secondary Objective

1. To assess the safety and reactogenicity of intradermal administration of Qdenga.

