Another study evaluated the safety and immunogenicity of an early low-dose tetravalent dengue vaccine candidate (LD-TDV), which uses an attenuated serotype 2 backbone, administered intradermally either with an injector device (PharmaJet) or a needle-syringe in 67 subjects. The findings indicated that the intradermal administration of LD-TDV was well tolerated, with no significant safety concerns, and induced an immune response against all four dengue serotypes. The overall tetravalent seroconversion rates were 13.8% at Day 28 and 31.0% at Day 118, comparable to the previously reported 25% seroconversion rate for low-dose TDV given intradermally in 72 flavivirus-naive adults. Local reactions, such as induration (91.7% vs. 12.5%;  $P < .0001$ ) and pruritus (50% vs. 8.3%;  $P = .0034$ ), were more frequent following intradermal vaccination compared to subcutaneous administration. Most of these reactions were mild and resolved within one day.

This study aims to ensure the safety of vaccine recipients by comparing the administration of a second dose via the intradermal (ID) route after an initial subcutaneous (SC) dose with a control group receiving both doses subcutaneously (SC-SC). Previous research in Thailand on COVID-19 vaccines also evaluated the safety and immunogenicity of fractional (1/5th or 1/6th) doses of homologous ChAdOx1 or BNT162b2 administered intradermally following an initial intramuscular (IM) dose, demonstrating safety and immunogenicity. Based on this, the study hypothesizes that intradermal administration of fractional doses of the Qdenga vaccine after an initial SC dose will be immunogenic and have acceptable systemic adverse effects, with potential utility as a booster in the future.

The potential of intradermal vaccination to maintain or enhance immunogenicity while reducing the required dose has been highlighted in several reviews. This method could lower costs and improve vaccine accessibility in low-resource settings. However, further research is needed, as no randomized studies have yet evaluated both humoral and cell-mediated immune responses to intradermal Qdenga vaccination.

[figure not shown]

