#### **5.7.6 Sample size calculation**

In this study, a total sample size of 24 participants will be used, allocated equally into two groups of 12 participants each. Based on the recommendation by Julious, a sample size of 12 subjects per group is considered adequate to achieve reasonable precision for preliminary estimates in a pilot study.

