### 5.7.8 Study variables and their definition

Independent variables

- Technique of vaccination: subcutaneous vs. intradermal
- Sex
- Age

Dependent variables

- ELISA: Antibody level for dengue at day 0, 30, 120
- ELISpot: T cell responses against dengue antigens at day 0, 30, 120
- Adverse event following vaccine (AEFI)

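### Adverse events get only percentages and a difference test, with no interval; at 12 per arm a non-significant result cannot support a claim of acceptable adverse effects

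*Combined protocol and SAP*

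**What the plan says.** The Secondary Objective (section 5.4) is "To assess the safety and reactogenicity of intradermal administration of Qdenga". Section 5.7.8 lists adverse events following vaccination as a dependent variable, without further definition. The closing hypothesis in section 5.5 is that fractional intradermal doses after a subcutaneous first dose "will be immunogenic and have acceptable systemic adverse effects". No threshold, margin or reference rate is given for that.

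The analysis is in section 5.7.12, under Data analysis. It lists summaries and tests by type of variable and does not mention safety by name. For a yes/no adverse event it provides a percentage and this instruction: "Compare qualitative variables data using Pearson's Chi-squared test or Fisher's exact test". The significance rule is "A probability value (P) <0.05 was considered significant". The list contains no confidence interval, no rule for choosing between the two tests, and nothing on continuity correction.

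Section 5.7.6 fixes the size: "a total sample size of 24 participants will be used, allocated equally into two groups of 12 participants each". The stated reason is that 12 per group "is considered adequate to achieve reasonable precision for preliminary estimates in a pilot study". No power, effect size or event rate is attached to it.

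**The concern.** The study is sized for estimation, but for binary outcomes the plan commits only to a point percentage and a test of difference. A reader of the results would see, for example, 0% or 17% in the intradermal arm and a P value above 0.05, with nothing to show how wide a range of true rates fits those data. With 12 per arm, a moderate real increase in reactions will often be non-significant. Set beside a hypothesis of acceptable systemic effects that has no criterion, such a result is easily taken as support for the hypothesis, which it is not.

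A lesser matter is that two tests are allowed with no rule for choosing. If the uncorrected Pearson test is one of them, some borderline tables can be called significant or not according to a choice made after the data are seen.

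**Working it through.** **Inputs.** 12 per arm (5.7.6); threshold 0.05 (5.7.12); intradermal v subcutaneous rates for induration (91.7% v 12.5%) and pruritus (50% v 8.3%) (5.5). Assumed: two-sided tests, because sidedness is not stated; no dropout; each event type reduced to yes/no per participant.

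**The plan's own figure.** 12 + 12 = 24. This is a pilot rule of thumb, so there is no formula to reproduce.

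**1. What zero or few events leave open.** For 0/12 the exact (Clopper-Pearson) two-sided 95% upper limit is 1 − 0.025^(1/12) = 0.265. The exact intervals are:

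| Observed | 95% CI |
|---|---|
| 0/12 | 0% to 26.5% |
| 1/12 | 0.2% to 38.5% |
| 2/12 | 2.1% to 48.4% |

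If the true rate were 10%, no events would still be seen with probability 0.9^12 = 0.28.

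**2. What equal observed rates leave open.** Newcombe's 95% interval for the risk difference combines the two Wilson intervals. For 0/12 the Wilson upper limit is 1.96²/(12 + 1.96²) = 3.84/15.84 = 0.242, so 0/12 v 0/12 gives −24.2 to +24.2 percentage points. For 2/12 v 2/12 it is −30.6 to +30.6 points. Both tables have P = 1 by Fisher.

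**3. Power of Fisher's test.** Power is the sum, over all tables (a, b) with Fisher P<0.05, of Bin(a; 12, p_ID) × Bin(b; 12, p_SC).

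| Rates, ID v SC | Source | Fisher power |
|---|---|---|
| 91.7% v 12.5% (induration) | 5.5 | 99% |
| 50% v 8.3% (pruritus) | 5.5 | 47.5% |
| 30% v 10% | assumed | 9.5% |
| 40% v 10% | assumed | 23.3% |
| 50% v 10% | assumed | 42.5% |

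The last three rows are illustrations only, because the documents give no systemic adverse-event rate by route. With 0/12 in the subcutaneous arm, Fisher needs 5/12 in the intradermal arm: 4/12 v 0/12 gives 2 × 495/10,626 = 0.093, and 5/12 v 0/12 gives 2 × 792/42,504 = 0.037.

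**4. The open choice of test.** There are 13 × 13 = 169 possible tables. Uncorrected Pearson gives P<0.05 in 76 and Fisher in 60. The 16 discordant tables are all significant by Pearson only. One of them matches the cited pruritus rates, 6/12 v 1/12:

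- Uncorrected Pearson: 24 × (6×11 − 6×1)²/(12×12×7×17) = 86,400/17,136 = 5.04, P = 0.025.
- Fisher: 2 × (924×12 + 792)/346,104 = 0.069.
- Continuity-corrected Pearson: 24 × (60 − 12)²/17,136 = 3.23, P = 0.072.

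The corrected test disagrees with Fisher in 0 of 169 tables. The maximum type I error (common rate on a 0.01 grid) is 6.4% for uncorrected Pearson and 2.3% for both Fisher and the corrected test. At true rates of 50% v 8.3%, the chance of a table on which uncorrected Pearson and Fisher disagree is 17.4%.

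**The case against.** **The test conflict is narrow.** A reader might infer that the two permitted tests generally give opposite answers. They do not. The plan names R, whose default test for a 2×2 table applies the continuity correction (checked in version 4.3.3; the plan's 3.5.1 was not available), and that removes every conflict with Fisher. The common convention of using Fisher when an expected count is below 5, which the plan does not state, would settle 12 of the 16 discordant tables. It leaves 8 v 3 and 9 v 4, in either order, and the chance of meeting one of those at 50% v 8.3% is about 0.8%. This objection stands. What remains is that the plan states neither the convention nor the correction.

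**The plan does not say that safety will be judged by a P value.** That would be an inference from a generic list that also gives percentages. Safety is a secondary objective to be assessed, in a pilot, and the wording on acceptability comes from the literature review. Nothing says that P>0.05 will be read as acceptable. This also stands. The point is only that no other analysis is provided for adverse events.

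**The comparison is not useless.** At the cited induration rates, power is about 99%. A claim that the safety comparison is uninformative in general would be wrong. Nor is the route untested, since section 5.5 describes earlier intradermal studies of this vaccine or its early low-dose candidate.

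**Intervals could appear anyway.** R's Fisher routine returns an interval for the odds ratio by default. But the plan does not commit to reporting it, and an odds ratio does not tell a reader what event rate is still possible.

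**There is already a numerical limit.** Section 5.7.5 has a termination criterion of more than 10% for severe local events. It concerns a different kind of event and does not define acceptable systemic effects.

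**Conclusion.** The concern holds as a gap in estimation and interpretation. The single analysis that reaches the safety objective provides percentages and a difference test and no measure of precision, which does not match the plan's own reason for 12 per arm. A non-significant result cannot support acceptable systemic adverse effects, because no criterion is set and because the data leave so much open: up to 26.5% after no events in 12, and about 30 points either way after 2/12 in each arm. Large differences, such as the cited induration rates, would be detected. Differences like the cited pruritus rates would be missed about half the time (1 − 0.475 = 0.525).

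The open choice of test is secondary: 16 of 169 tables if Pearson is uncorrected, none under R's default.

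This rests on two-sided testing and 12 evaluable participants per arm. The cited rates are for local reactions in an earlier study, so they show the scale of the problem and do not predict this trial's results.

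**What to change.** In section 5.7.12:

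- Report each adverse-event type by arm as the proportion of participants affected, with an exact (Clopper-Pearson) 95% CI.
- Report the risk difference with a 95% CI, for example Newcombe's.
- State that safety is descriptive, and that P>0.05 will not be read as evidence of acceptable safety.
- If a P value is kept, name Fisher's exact test for all binary outcomes. Make the interval the main summary, because the two can differ over zero: for 6/12 v 1/12 Newcombe gives 5.1 to 67.2 points while Fisher gives P = 0.069.
- State that no events in 12 recipients excludes only rates above about 26%.

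No change to the design, sample size or data collection is needed. The cost is a few lines of R and a safety statement that reads less favourably than a bare percentage with a non-significant P value.
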